10. EXPLORATORY BIOLOGICAL STUDIES

Biological studies are an important, but optional part of the trial. We will be collecting two types of sample: formalin fixed paraffin embedded tissue (bone marrow and lymph nodes) and blood.

The objective for the translational studies is to identify biomarkers of immunological response to the combination of pembrolizumab and rituximab in patients with relapsed/refractory WM. The translational research aims to inform our understanding of which patients respond to therapy and the underlying mechanisms of response to study treatment.

The following exploratory endpoints will be assessed:

- Assessment of PD-1 and PD-L1/ PD-L2 expression by FISH and immunohistochemistry (IHC). A positive correlation between high PD-L1 expression levels and responses to PD-1 inhibitors has been seen in advanced stage Hodgkin lymphoma patients); this would allow assessment of whether response to PD-1 inhibitors in WM is mediated by a similar mechanism. Assessment of the distribution of expression of PD-1 and PD-L1/ PD-L2 by IHC would further explore the hypothesis that signalling through this pathway contributes to the facilitative effect of the tumour microenvironment, and whether PD-1 inhibitors abrogate this interaction
- IHC to assess baseline and on-treatment changes to distribution and composition of immune response cells in the microenvironment
- Analysis of baseline biopsies (where available) to elucidate potential mechanisms of action of tumour response
- Assessment of treatment outcome according to tumour genotype, as determined by a Next Generation Sequencing (NGS) panel to include mutations in MYD88, CXCR4, TP53, BTK and PLC γ gamma.
- Correlation of bone marrow response with reduction in serum IgM level. Previous studies have shown that there can be a discrepant response between the IgM and bone marrow
- Quantification of bone marrow involvement by morphologic assessment of trephine and flow cytometric assessment of aspirate for MRD with correlative assessment of MRD on peripheral blood at the same timepoints

Procedures to determine disease response assessment are mandatory in the trial as outlined in the Assessments section 9, however providing samples for the biological studies is **optional** to the patient. Additional samples should only be obtained from consenting patients. Patients who do not give their consent to donate the optional samples can still take part in the trial.

The Haematological Malignancy Diagnostic Service (HMDS) in Leeds will be responsible for analysis of the optional samples.

UCL CTC will inform HMDS if a patient has given consent for samples to be analysed as part of the trial and whether they have consented for surplus samples to be stored for future ethically approved research. Laboratory processing of any samples will not occur until patient consent has been confirmed. Please refer to the laboratory manual for details of how to send and log samples. Patients must be pre-registered and assigned a trial number before any samples are sent to HMDS.

We will be collecting four types of sample: lymph node biopsy (in FFPE), bone marrow aspirates trephine (in FFPE), bone marrow aspirate and peripheral blood.

Sites must keep a record of all samples sent to HMDS. See the Laboratory Manual for more details of how to track samples.

10.1. Lymph node and bone marrow trephine formalin fixed paraffin embedded blocks – optional to patient

In all patients, a bone marrow trephine sample should be obtained at pre-registration within 28 days prior to starting treatment.

In patients with nodal disease, a lymph node biopsy sample at pre-registration should also be taken. Preferably the nodal biopsy should be obtained within 28 days prior to C1D1. If not possible, then historical lymph node biopsy tissue may be sent.

Formalin fixed paraffin embedded (FFPE) tissue from the bone marrow trephine and lymph node should be sent to HMDS, Leeds. Please see the laboratory manual for further details of how to send

3µm sections of the tissue block will be taken and immunohistochemistry performed. At least ten markers will be assessed for each case including: CD5, CD10, CD79a, CD56, CD20, CD38, PD1, PD-L1, PD-L2. For PD-L1 and PD-L2, the percentage of malignant and non-malignant cells with positive staining will be reported and a central pathological report provided.

GEP will be performed using the HTG Immunopanel and the Affymetrix Human Transcriptome Array, which is a whole transcriptome array. These are two gene expression platforms currently being used in HMDS with bioinformatic support from within HMDS and in collaboration with the University of Leeds. The panel will include mutations in MYD88, CXCR4, TP53, BTK and PLC γ

Once analysis is complete, blocks can be returned to sites at their request.

10.2. Bone marrow samples – optional to patient

Research bone marrow aspirate samples will be obtained at the following time points:

Time point	Sample required
Pre-registration (up to 28 days prior to starting treatment)	5 ml bone marrow aspirate in EDTA
Week 24 post commencing treatment	5 ml bone marrow aspirate in EDTA
1 year post commencing treatment	5 ml bone marrow aspirate in EDTA

Multicolour flow panels will be performed on the marrow to identify the flow cytometry phenotype, with further samples taken halfway and at the end of therapy to assess minimum residual disease in bone marrow.

Bone marrow samples, or any products produced from these, will not be returned to sites.

10.3. Peripheral blood samples – optional to patient

Research peripheral blood samples will be obtained at the following time points:

Time point	Sample required
Pre-registration (up to 28 days prior to starting treatment)	20 (4 x 5) ml peripheral blood in EDTA
Week 24 post commencing treatment	20 (4 x 5) ml peripheral blood in EDTA
1 year post commencing treatment	20 (4 x 5) ml peripheral blood in EDTA

Multicolour flow panels will be performed on blood on the baseline sample to identify the flow cytometry phenotype, with further samples taken halfway through and at the end of therapy to assess minimal residual disease in peripheral blood.

Blood samples, or any products produced from these, will not be returned to sites.

11. DATA MANAGEMENT AND DATA HANDLING GUIDELINES

Data will be collected from sites on version controlled case report forms (CRFs) designed for the trial and supplied by UCL CTC. Data must be accurately transcribed onto trial CRFs and must be verifiable from source data at site. Examples of source documents are hospital records which include patient's medical notes, laboratory and other clinical reports etc.

Where copies of supporting source documentation (e.g. autopsy reports, pathology reports, CT scan images etc.) are being submitted to UCL CTC, the patient's trial number must be clearly indicated on all material and any patient identifiers removed/blacked out prior to sending to maintain confidentiality.

Please note that, for this trial, patients must consent to their NHS/CHI number being supplied to UCL CTC. This is required in order to allow for follow up via national registries where needed.

11.1. Completing Case Report Forms

All CRFs must be completed and signed by staff who are listed on the site staff delegation log and authorised by the PI to perform this duty. The PI is responsible for the accuracy of all data reported in the CRF.

All entries must be clear, legible and written in ballpoint pen. Any corrections made to a CRF at site must be made by drawing a single line through the incorrect item ensuring that the previous entry is not obscured. Each correction must be dated and initialed. Correction fluid must not be used.

The use of abbreviations and acronyms should be avoided.

11.2. Missing Data

To avoid the need for unnecessary data queries CRFs must be checked at site to ensure there are no blank fields before sending to UCL CTC (unless it is specifically stated that a field may be left blank). When data are unavailable because a measure has not been taken or test not performed, enter "ND" for not done. If an item was not required at the particular time the form relates to, enter "NA" for not applicable. When data are unknown enter the value "NK" (only use if every effort has been made to obtain the data).

11.3. Timelines for Data Return

CRFs must be completed at site and returned to UCL CTC as soon as possible after the relevant visit and within 4 weeks of the patient being seen. Registration forms should be faxed/mailed to UCL CTC. Death forms and SAE reports should be returned within 24 hours by fax/email.

Sites that persistently do not return data within the required timelines may be suspended from recruiting further patients into the trial by UCL CTC and subjected to a 'triggered' monitoring visit. See section 14.3 ('Triggered' On-Site/Remote Monitoring) for details.

11.4. Data Queries

Data arriving at UCL CTC will be checked for legibility, completeness, accuracy and consistency, including checks for missing or unusual values. Data Clarification Requests will be sent to the data contact at site. Further guidance on how data contacts should respond to data queries can be found on the Data Clarification Request forms.

12. PHARMACOVIGILANCE

12.1. Definitions

The following definitions have been adapted from Directive 2001/20/EC, ICH E2A “Clinical Safety Data Management: Definitions and Standards for Expedited Reporting” and ICH GCP E6.

Adverse Event (AE)

Any untoward medical occurrence in a patient treated on a trial protocol, which does not necessarily have a causal relationship with an IMP. An AE can therefore be any unfavourable and unintended sign (including an abnormal laboratory finding), symptom or disease temporally associated with the use of an IMP, whether or not related to that IMP. See section 12.2.1 for AE reporting procedures.

Adverse Reaction (AR)

All untoward and unintended responses to an IMP related to any dose administered. A causal relationship between an IMP and an adverse event is at least a reasonable possibility, i.e. the relationship cannot be ruled out.

Serious Adverse Event (SAE) or Serious Adverse Reaction (SAR)

An adverse event or adverse reaction that at any dose:

- Results in death
- Is life threatening (the term “life-threatening” refers to an event in which the patient was at risk of death at the time of the event. It does not refer to an event that hypothetically might have caused death if it were more severe)
- Requires in-patient hospitalisation or prolongs existing hospitalisation
- Results in persistent or significant disability/incapacity
- Is a congenital anomaly or birth defect
- Is otherwise medically significant (e.g. important medical events that may not be immediately life-threatening or result in death or hospitalisation but may jeopardise the patient or may require intervention to prevent one of the other outcomes listed above)

See section 12.2.2 for SAE reporting procedures.

Suspected Unexpected Serious Adverse Reaction (SUSAR)

A serious adverse reaction, the nature or severity of which is not consistent with the applicable reference safety information.

i.e. an adverse event that meets all the following criteria:

- Serious – meets one or more of the serious criteria, listed under the definition of SAE above
- Related – assessed by the local PI or designee, or Sponsor as causally related to one or more elements of the trial treatment

- Unexpected – the event is not consistent with the applicable reference safety information

See section 12.3 for reporting procedures for these events.

Adverse event of special interest (AESI)

An AE that is of scientific and medical concern to the Trial Management Group and MSD for which rapid communication is required. The AESI may not meet the standard criteria for seriousness and it may occur outside the standard AE reporting timeframes for the trial.

See section 12.4 for the list of AESI for the trial and their reporting procedures for these events.

Urgent event

An AE that is protocol-related and requires completion of a trial specific Case Report Form.

See section 12.5 for a list of and reporting procedures for these events.

Overdose, Trial treatment error, or Occupational exposure

Refer to section 8.6 for details on reporting of these events.

12.2. Reporting Procedures

Adverse Event Term

An adverse event term must be provided for each adverse event. Wherever possible a valid term listed in the Common Terminology Criteria for Adverse Events (CTCAE) v5.0 should be used. This is available online at:

https://ctep.cancer.gov/protocoldevelopment/electronic_applications/docs/CTCAE_v5_Quick_Reference_8.5x11.pdf

Severity grade of each adverse event must be determined by using CTCAE v5.

Causality

The relationship between the treatment and an adverse event will be assessed.

For AEs (including SAEs), the local PI or designee will assess whether the event is causally related to each IMP.

For SAEs, a review will also be carried out by the Sponsor's delegate.

Causal relationship to each trial treatment must be determined as follows:

- Related (reasonable possibility) to an IMP
- Not related (no reasonable possibility) to an IMP

UCL CTC will consider events evaluated as related to be adverse reactions.

12.2.1. Reporting of Adverse Events (AEs)

All adverse events that occur between informed consent and 5 months post last IMP administration must be recorded in the patient medical notes and the trial CRFs.

An AE cover sheet should be completed and a photocopy submitted to UCL CTC at each trial visit. The Adverse Event form should be submitted when there are new AEs or changes to existing AEs on the form. Any updates or changes to previously reported AEs must be initialed and dated. Report the worst grade observed for the AE on the form.

Those meeting the definition of a Serious Adverse Event (SAE) or Adverse Event of Special Interest (AESI) must also be reported to UCL CTC using the trial specific SAE Report. Also refer to section 12.2.2 (Reporting of Serious Adverse Events (SAEs)) and section 12.4 (Adverse Events of Special Interest)). Adverse events meeting the definition of an Urgent Event must be reported on an Urgent Event form (see section 12.5 Urgent Events).

Pre-existing conditions (i.e. conditions present at registration) do not qualify as adverse events unless they worsen or recur (i.e. improves/resolves and then worsens/reappears again).

E.g. an AE could be an exacerbation of a chronic or intermittent pre-existing condition including either an increase in frequency and/or intensity of the condition (worsening of the event). Another example of an AE is when a pre-existing condition improves during the trial (e.g. from grade 3 to grade 1) and then it worsens again (e.g. from grade 1 to grade 2), even if the event is of severity equal or lower to the original condition (improvement and recurrence of the event).

NB the disease(s) under study and its anticipated day-to-day fluctuations would not be an AE.

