9.2.1. Assessments prior to each cycle of treatment

The following assessments should be performed within 3 days prior to each cycle:

- Clinical examination: physical examination (including assessment of lymph node, liver and spleen size)
- Concurrent medication assessment
- Adverse event assessment
- Observations: pulse, temperature, blood pressure, oxygen saturations
- Weight
- Assessment of ECOG performance status (see appendix 3)
- Full blood count (including red blood cell (RBC), haemoglobin (Hb), white blood cell (WBC) absolute neutrophil count (ANC), absolute lymphocyte count (ALC), haematocrit and platelets)
- Biochemistry (including bicarbonate, uric acid, albumin, alkaline phosphatase (ALP), alanine/aspartate transaminase (ALT/AST), total bilirubin, calcium, creatinine, potassium, sodium, glucose, urea, and estimated glomerular filtration rate (eGFR), U&E, liver function tests (LFT), and amylase)
- Electrocardiogram (ECG)
- Serum IgM, IgG and IgA
- Serum paraprotein
- Serum immunofixation (only to be performed if paraprotein not detectable)
- TSH, glucose and ACTH tests
- Highly sensitive urine or serum pregnancy test in women of childbearing potential (WOCBP)

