15.2. Discontinuation of Trial Treatment

A patient may be withdrawn from trial treatment whenever such treatment is no longer in the patient's best interests, but the reasons for doing so must be recorded in the patient's medical notes and on the relevant Case Report Form(s). Reasons for discontinuing treatment may include:

- Disease progression whilst on therapy
- Unacceptable toxicity (see section 8.5 for full details)
- Intercurrent illness which prevents further treatment
- Patient decision not to continue with trial treatment
- Any alterations in the patient's condition which justifies the discontinuation of treatment in the site investigator's opinion
- Non-compliance with the trial treatment and/or procedures
- If a female patient becomes pregnant or male/female fails to use adequate birth control (for patients of childbearing potential)

In these cases patients will remain within the trial for the purposes of follow-up and data analysis unless they explicitly withdraw consent. See section 9 for details.

If a patient expresses their wish to withdraw from trial treatment, sites should explain the importance of remaining on trial follow-up, or failing this of allowing routine follow-up data to be used for trial purposes and for allowing existing collected data to be used. If the patient gives a reason for wishing to discontinue treatment, this should be recorded.

The following CRFs should be submitted if a patient discontinues trial treatment early:

- Treatment summary form
- Treatment forms for all cycles of treatment received
- Rolling AE form for all cycles of treatment received

Thereafter, unless the patient has withdrawn consent, the site should report AEs/SAEs and submit relevant follow up forms.

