17.2.2. Analysis of secondary endpoints and secondary analyses

Safety and tolerability of pembrolizumab in combination with rituximab

As this is continuous treatment, care will be taken to assess the burden of adverse events over time rather than just the worst grades seen.

Rates of adverse events (as assessed by CTCAE version 5.0) will be presented in four ways:

1. Worst grade seen of each event, i.e. the number of patients who experience a grade 1-2 or 3+ event at any time point.
2. Worst grade seen of each event per cycle, i.e. the number of patients who experience a grade 1-2 or 3+ event during each cycle.
3. Proportion of cycles where patients experience a grade 1-2 or grade 3-4 AE. This may also be presented by the number of cycles depending on the numbers of patients stopping treatment.
4. Median number of grade 1-2 or 3+ AEs (of any type) experienced at each cycle.

Analyses 3-4 may focus on clinical events only i.e. excluding lower level biochemical and haematological events which may not have an impact on the patient's quality of life.

Depending on the frequency of adverse events, we may also look at duration of some events, possibly as a proportion of the time on treatment.

AEs of special interest will be reported in more detail, with events of any grade presented.

All adverse event analysis will be descriptive.

Best response and time to best response.

The best response is the best response seen from the start of treatment; all response time points will be included.

Time to maximal response to treatment will be calculated as the time from the date of registration until the date of the best response. This will be presented as the median and range and will be reported for responding patients only.

Time to next treatment

Time to next treatment will be analysed using Kaplan-Meier survival analyses, with the time calculated from the date of registration to the date of the start of the next line of therapy. Patients who do not start a further line of treatment will be censored at the date last seen/date of death. The median (if applicable) and rates at 1 and 2 years will be presented.

Progression free survival

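### Section 12.2.1 does not require the per-cycle adverse event grade that three of the four safety presentations in 17.2.2 need

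*Combined protocol and SAP*

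**What the plan says.** **Collection (12.2.1, 15.2, 9.2.1).** Section 12.2.1 gives one grading instruction: "Report the worst grade observed for the AE on the form". On timing it says: "An AE cover sheet should be completed and a photocopy submitted to UCL CTC at each trial visit"; and "The Adverse Event form should be submitted when there are new AEs or changes to existing AEs on the form". On amendments it says: "Any updates or changes to previously reported AEs must be initialed and dated". Section 15.2 describes the form as a "Rolling AE form for all cycles of treatment received". Section 9.2.1 includes an AE assessment among the checks made in the 3 days before every cycle.

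**Analysis (17.2.2).** Because treatment is continuous, the plan states that "care will be taken to assess the burden of adverse events over time rather than just the worst grades seen". It then lists four presentations. The first is the worst grade at any time. The second is: "Worst grade seen of each event per cycle, i.e. the number of patients who experience a grade 1-2 or 3+ event during each cycle". The third is the proportion of cycles in each grade band, and the fourth is the median number of AEs in each grade band at each cycle. The section may also look at how long some events last. All AE analysis is to be descriptive.

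**The concern.** Presentations 2, 3 and 4 need to know the grade an event had in each cycle. On its natural reading for a rolling form, the instruction in 12.2.1 yields one grade per event, namely its peak. The dated-update rule helps only in one direction. When an event worsens, its worst grade changes and the change is dated. When it improves, its worst grade is unchanged, so nothing on the form has to change until the event ends.

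Falls in grade are to be expected in this protocol. Sections 8.4.2 and 8.4.4 tie the restart of withheld treatment to the event having come down to grade 1 or 0. A patient can therefore begin further cycles with an open grade 1 event whose recorded grade is still 3. With up to 18 cycles, this is the kind of course that a burden-over-time analysis is meant to show.

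Safety and tolerability belong to the overall aim and are the first-listed secondary endpoint. If the data hold only peak grades, the tables meant to go beyond worst grades would largely restate them.

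**Working it through.** The plan states no figure on this point, so there is none to reproduce. The check sets the collection rule against each presentation and then counts cycles for a hypothetical event.

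**Step 1. What each presentation needs**

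| Presentation (17.2.2) | Grade needed | Required by 12.2.1? |
|---|---|---|
| 1. Worst grade at any time | Peak grade per event | Yes |
| 2. Worst grade per cycle | Grade in each cycle | Rises dated; falls not required |
| 3. Proportion of cycles by grade band | Grade in each cycle | Rises dated; falls not required |
| 4. Number of AEs by grade band per cycle | Grade in each cycle | Rises dated; falls not required |

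Neither section says how a cycle's grade is derived from the form.

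**Step 2. Three plausible derivation rules**

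Let an AE be at grade 1-2 for *a* cycles, then at grade 3+ for *g* cycles, then at grade 1-2 for *b* cycles. The true number of grade 3+ cycles is *g*.

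- Rule A, worst grade in every open cycle: a + g + b
- Rule B, worst grade from the dated rise until resolution: g + b
- Rule C, worst grade in the onset cycle only: 1

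**Step 3. Numbers (all durations are assumptions)**

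| a, g, b | True | Rule A | Rule B | Rule C |
|---|---|---|---|---|
| 2, 1, 3 | 1 | 6 | 4 | 1 (wrong cycle) |
| 0, 1, 5 | 1 | 6 | 6 | 1 |
| 5, 1, 0 | 1 | 6 | 1 | 1 (wrong cycle) |
| 3, 2, 0 | 2 | 5 | 2 | 1 (wrong cycle) |
| 0, 4, 0 | 4 | 4 | 4 | 1 |

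In the first row the true number of grade 1-2 cycles is 2 + 3 = 5. Rule A leaves 6 - 6 = 0 and rule B leaves 6 - 4 = 2, so the lower band is understated by what the upper band gains.

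The last three rows show the limits. Rule B is exact when the grade is constant or only rises. Rule A is exact only when the grade is constant. Rule C understates any event that stays at grade 3+ for more than one cycle.

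**Step 4. Range**

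Under rule A the overstatement factor is (a + g + b)/g. With one true grade 3+ cycle out of 18 (1/18 = 5.6%), an AE open for 2, 6 or 18 cycles gives:

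- 2 cycles: factor 2, and 2/18 = 11%
- 6 cycles: factor 6, and 6/18 = 33%
- 18 cycles: factor 18, and 18/18 = 100%

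**The case against.** The strongest reply is that the form itself cannot be inspected. The AE form, cover sheet and treatment forms are not in the documents. A cover sheet goes in at each visit, the AE form is resubmitted on change, and updates are dated. Any of these might carry a grade per visit. The instruction is also open to another reading: it follows sentences about visit-by-visit submission and could mean the worst grade in the reporting interval, which is what presentation 2 needs. Sites must in any case assess falls in grade to decide on restarting withheld treatment, AEs go into the medical notes, and data queries are possible.

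This stands as a limit on the claim. A reader might infer that the form records only the peak grade and that presentations 2 to 4 cannot be derived. The documents do not support that, because partial reconstruction from dated changes is possible and the form may hold more. A reader might also infer that grade 3+ cycles would necessarily be overstated. That does not follow either: 17.2.2 gives no derivation rule, and onset-only placement can understate. Nor would resolution be hidden. The possible analysis of duration implies start and stop dates, and with those the count of AEs of any grade per cycle survives.

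What the reply does not do is close the gap. No text requires a fall in an on-trial AE to reach the form. The example in 12.2.1 of an event that improves and then worsens concerns conditions present at registration. Assessing a fall at site is not the same as reporting it. If the instruction was meant per interval, it should say so.

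**Conclusion.** The point holds in conditional form. The stated collection rule does not require the per-cycle grade that presentations 2 to 4 use, and it sits against the stated aim of looking beyond worst grades. If the form already captures grade per cycle or dated falls, the problem is one of wording only. If it does not, those presentations will misplace grade 3+ cycles. Carrying the worst grade to resolution overstates them and understates grade 1-2 cycles; placing it at onset alone can understate them.

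The 6, 4 or 1 in the worked example is an illustration for one assumed event, not an estimate for the trial. The documents give no AE durations, so the net effect on the tables cannot be sized. The consequence is bounded: the affected analyses are secondary and descriptive, presentation 1 and the primary endpoint are untouched, and the numeric review trigger in 17.3 counts treatment-related deaths, not AE grades. It is still worth correcting, because a stated collection rule and the stated analyses of a named endpoint do not match.

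**What to change.** - Check the AE form and cover sheet first. If either already records a grade per cycle or every dated grade change, amend 12.2.1 to say so.
- Otherwise, change 12.2.1 and the rolling AE form so that sites enter the worst grade within each cycle for every ongoing AE, or start a new dated line at every grade change, up or down. The AE assessment already required before each cycle in 9.2.1 supplies the information.
- Derive the overall worst grade for presentation 1 from these entries.
- State in 17.2.2 how a grade is assigned to a cycle, including how time in a delayed cycle is counted.

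The cost is a form revision and slightly more data entry at visits that already take place. For patients already treated, any fall that was not entered would have to be retrieved from the medical notes. Where that is not done, the report should name the rule used and say which way it can err.
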